10.6 Assessment of Metformin Associated Lactic Acidosis (MALA)

In order to assess acid-base status in treated patients and in order to limit the patient discomfort, peripheral venous blood gas analysis (pVBGA) will be performed during scheduled and unscheduled visits.

The appearance of any suspicious symptom or sign should trigger prompt testing (pVBGA) (i.e., within 24 hours). Local laboratory testing is always permitted.

The investigator must follow the following rules:

lactate level is between 2-4 mmol/l and pH over 7.35, pVBGA has to be promptly repeated within 24 hours. If confirmed, patient has to reduce metformin dosage (from 1500 mg a day to 1000 mg a day or from 1000 mg a day to 500 mg a day). pVBGA has to be repeated every other day for 1 week till normalization. Once restored normal values, patient can uptitrate to the former dosage and pVBGA has to be retested after 7 days. If normal, patient can keep on treatment, otherwise meformin dosage has to be reduced as previously described till normalization. In this case higher dosage can not be restored.

In both cases, if pVBGA fail to restore, metformin has to be permanently stopped. In this case, EoTx visit has to be collected and the patient has to be followed up for 21 days.

 lactate level is higher than 4 mmol/l with sVO₂ between 30-50% (irrespective of pH) or lactate between 2-4 mmol/l but associated to pH lower than 7.35. In these cases IMP must be suspended and patient hospitalized. If AEs fails to recover in 3 weeks, IMP must be permanently discontinued.

Once AEs recovered the patient can undergo IMP re-challenge, by restarting since metformin titration. In this case pVBGA has to be performed every week prior to up-titration. If pVBGA is normal, the patient can uptitrate, otherwise meformin dosage has to be reduced till the minimum allowed dosage (that is 1000 mg a day) as previously described till normalization.

If pVBGA fail to restore, metformin has to be permanently stopped. In this case, EoTx visit has to be collected and the patient has to be followed up for 21 days.

10.7 Assesment of Metformin Associated Megaloblastic Anemia (MAMA)

The pathogenic mechanisms of vitamin B_{12} deficiency in metformin treatment have not been fully elucidated. However, among the instances of bacterial overgrowth in the small intestine attributable to diabetes mellitus, changes in small bowel motility, alterations in the bacterial flora, competitive inhibition, the inactivation of vitamin B_{12} absorption, or the effect of calcium on cell membranes have been suggested to play a role.

Vitamin B_{12} deficiency is clinically important because it is a reversible cause of bone marrow failure and demyelinating nerve disease. Neurologic damage, a possible consequence of metformin-induced vitamin B_{12} deficiency, can present as peripheral neuropathy and may be mistaken for diabetic neuropathy in patients on metformin treatment.

Some studies (81–83) showed a clear relationship between the dosage or duration of metformin use and vitamin B_{12} deficiency in patients with type 2 diabetes, with an incidence of 19% after 4 years of treatment. Subjects with metformin use ≥10 years and daily dosage ≥2,000 mg show about a 4-fold higher risk of vitamin B_{12} deficiency compared to those with metformin use of <4 years and daily dosage of ≤1,000 mg. The presence of anemia shows a statistically positive association with vitamin B_{12} deficiency.

For these reasons Cianocobalamin blood dosage and Complete Blood Count will be regularly performed. In case of Cianocobalamin deficiency onset, oral supplementation will be allowed.

11. TREATMENT/STUDY DISCONTINUATION

Patients should be informed of circumstances under which their participation may be terminated by the Investigator without their consent.

A subject may temporarily or permanently discontinue IMP for a number of reasons listed below:

- 1. Reasons related to AE:
 - a. Subject could not tolerate IMP due to an AE which is annoying or uncomfortable but not serious or hazardous,
 - Physician determined that there are potential IMP related safety concern or SAE placing subject at undue hazard,
 - c. Serious adverse event (SAE),
 - d. Progression of disease leading to dialysis, transplantation or eGFR decline as determined by the investigator,
 - e. Blood Venous Gas abnormalities meeting criteria for MALA,
 - f. Clinical signs of MALA,
 - g. Fever or diarrhea,
 - h. Liver test abnormalities meeting criteria for permanent discontinuation,
 - i. Clinical signs of DILI (e.g., jaundice, right upper quadrant pain).
- 2. Death;
- 3. Reasons unrelated to medical condition (e.g., pregnancy, trial too burdensome);
- 4. Withdrawal of informed consent (partial related to IMP or complete from the trial);
- Lost to follow-up (detailed procedures to prevent subjects from becoming "lost to follow-up will be provided in the operations manual. These procedures must be followed by the investigator, their staff or other designated trial personnel);
- 6. Termination of all or part of the trial by the Promoter;
- Fall of eGFR below 15 ml/min (in case of tolvaptan treatment), below 30 ml/min (in case of metformin treatment);

8. Peripheral BVG predicting lactic acidosis onset (sVO2 between 30-50% and Lactate levels greater than 3,5 mmol/l; in this case ABG must be performed). In these cases IMP must be suspended for maximum 3 weeks and resumed once AEs recovered. If AEs fails to recover in 3 weeks, IMP must be permanently discontinued.

Any administrative or other reasons for withdrawal must be documented and explained to the patient.

If the reason for removal of a patient from the study is an AE, the principal specific event will be recorded on the eCRF. The patient should be followed until the AE has resolved, if possible. All patients will be followed for 21 days following the last dose of study medication-

If the subject temporarily interrupts or discontinues IMP due to an AE, the investigator, or other trial personnel, will make every effort to follow the event until it has resolved or stabilized.

If lost to follow-up, the Investigator should make every effort to contact the patient by telephone or by sending a registered letter to establish as completely as possible the reason for the withdrawal. A complete final evaluation at the time of the patient's withdrawal should be made with an explanation of why the patient is withdrawing from the study.

If the Promoter terminates or suspends the trial for safety or unanticipated other reasons, prompt notification will be given to investigators, IRBs/IECs, and regulatory authorities in accordance with regulatory requirements.

The Investigator will notify the Promoter promptly if the trial is terminated by the investigator or the IRB/IEC at the site. If the investigator, IRB/IEC or sponsor decides to terminate or suspend the trial's conduct at a particular center for safety, non-enrollment of

subjects, non-compliance with the protocol, or unanticipated other reasons, the above and other parties, as required by the applicable regulatory requirements, will be promptly notified.

If a subject discontinues during the screening period (because of consent withdrawal or failure to meet all of the requirements to continue in the trial) that subject will be considered a "Screen failure". Subjects who fail to meet trial requirements during the screening period may be rescreened at a later date.

Screen failure subjects will be recorded as such on the eCRF. Screening failure subjects do not require follow-up and can be considered for rescreening if the reason for the screen failure was not that the subject withdrew their consent. If rescreened, the subject will sign a new informed consent, will be assigned a new screening number, and will repeat all screening procedures.

If a subject discontinues during the IMP titration period or during the IMP Run-in period, that subject will be considered a "Titration failure" or a "Run-in failure".

Discontinuation during these two periods may be due to any of the following reasons:

- Subject does not meet entry requirements (i.e., subject cannot tolerate IMP treatment) as specified for a particular pre-randomization period;
- Subject decides to formally withdraw consent and/or fails to return for subsequent appointments at the trial site;
- Investigator considers the subject unsuitable for further participation.

"Titration failure" or a "Run-in failure" subjects will be recorded as such on the eCRF, they will complete an EoTx visit upon withdrawal from the trial.

The EoTx visit assessments will include:

1) Perform physical examination, including post-void body weight and height;

2) Record medical/PKD history;

3) Record concomitant medications and ensure subject's treatment meets current standard of care including lifestyle and dietary recommendations, especially for ingestion of at least2-3 liters of fluid per day as appropriate, unless otherwise directed by study doctor;

4) Assess AEs, if reported;

5) Assess vital signs (include heart rate and blood pressure);

6) Serum pregnancy test for WOCBP (second visit);

7) Collect urine and blood samples for clinical laboratory analyses, including serum creatinine, liver function tests, glucose metabolism parameter, CBC and venous gas analysis (second visit).

Run-in failure subjects will then be followed up after 7 days with a phone call to record any ongoing AEs; unless the subject fully withdraws consent to any further follow-up by written documentation

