10.1.3 Serious Adverse Event

A Serious Adverse Event (SAE) is any untoward medical occurrence that at any dose:

- results in death;
- is life-threatening (defined as an event in which the subject was at risk of death at the time of the event; it does not refer to an event which hypothetically might have caused death if it were more severe);
- requires inpatient hospitalization or causes prolongation of existing hospitalization;
- results in persistent or significant disability/incapacity;
- is a congenital anomaly/birth defect;

- is an important medical event (defined as a medical event(s) that may not be immediately life-threatening or result in death or hospitalization but, based upon appropriate medical and scientific judgment, may jeopardize the subject or may require intervention [e.g., medical, surgical] to prevent one of the other serious outcomes listed in the definition above.) Examples of such events include, but are not limited to, intensive treatment in an emergency room or at home for allergic bronchospasm; blood dyscrasias or convulsions that do not result in hospitalization);
- Transaminase levels raise above 5xUNL;
- Transaminase and total bilirubin 2xUNL;
- Clinical signs of Drug Induced Liver Injury (e.g., jaundice, right upper quadrant pain);
- Lactic Acidosis (as defined by pH<7,3 and Lactate> 4 mmol/l);
- Death;
- Pregnancy;
- Malignancies;
- Onset of permanent medical conditions contraindicating metformin or tolvaptan treatment (i.e.: myocardial infarction, severe chronic arrhythmias, chronic respiratory failure).

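### The lactate stopping rules in sections 10.6 and 11 contradict each other in one band and, above 4 mmol/l, miss results that meet the protocol's own definition of lactic acidosis

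*Combined protocol and SAP*

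**What the plan says.** Three parts of the protocol bear on a raised lactate.

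- **Section 10.6 (MALA assessment)** is binding: "The investigator must follow the following rules". Its first rule is: "lactate level is between 2-4 mmol/l and pH over 7.35, pVBGA has to be promptly repeated within 24 hours". If the repeat confirms the result, metformin is reduced by one step and treatment continues. This rule has no sVO2 condition. Its second rule covers lactate above 4 mmol/l with sVO2 "between 30-50% (irrespective of pH) or lactate between 2-4 mmol/l but associated to pH lower than 7.35". The action is: "In these cases IMP must be suspended and patient hospitalized".
- **Section 11, item 8** is triggered by "Peripheral BVG predicting lactic acidosis onset (sVO2 between 30-50% and Lactate levels greater than 3,5 mmol/l" and has no pH condition. An arterial gas is required, and then: "In these cases IMP must be suspended for maximum 3 weeks and resumed once AEs recovered".
- **Section 10.1.3 (serious adverse events)** lists "Lactic Acidosis (as defined by pH<7,3 and Lactate> 4 mmol/l", with no sVO2 condition.

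The list in section 11 that contains item 8 opens permissively: "A subject may temporarily or permanently discontinue IMP for a number of reasons listed below". Item 8 itself, however, uses mandatory wording.

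**The concern.** Two faults follow from reading these sections together.

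**Conflict.** In a narrow band of results, section 10.6 keeps the patient on metformin, at the current dose and then a reduced one, while item 8 takes the patient off it. Neither section refers to the other or says which prevails, so sites can act differently on the same blood gas.

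**Gap.** Above 4 mmol/l, both mandatory stops depend on sVO2 lying between 30 and 50%. Outside that window a patient can satisfy the protocol's definition of lactic acidosis and have no required suspension, while a patient with lower lactate and pH below 7.35 must be suspended and admitted. The written instruction weakens as lactate rises, and the protocol gives no reason for this.

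What is at stake is patient safety. Section 2.2.2 describes metformin associated lactic acidosis as rare but puts its mortality at around 50%.

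**Working it through.** There is no plan figure to reproduce. The check is to write each rule as a condition and see which ones apply.

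**Rules as written**

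- 10.6, reduce: lactate 2 to 4 and pH > 7.35 (any sVO2).
- 10.6, suspend and hospitalise: (lactate > 4 and sVO2 30 to 50%, any pH) or (lactate 2 to 4 and pH < 7.35, any sVO2).
- Item 8, suspend and arterial gas: lactate > 3.5 and sVO2 30 to 50% (any pH).
- 10.1.3, lactic acidosis: lactate > 4 and pH < 7.3 (any sVO2).

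**Applied to example results**

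| Lactate (mmol/l) | pH | sVO2 (%) | Section 10.6 | Section 11, item 8 | Meets 10.1.3 definition |
|---|---|---|---|---|---|
| 3.6 or 4.0 | 7.40 | 40 | repeat, then reduce | suspend, arterial gas | no |
| 3.6 or 4.0 | 7.40 | 25 or 65 | repeat, then reduce | no rule | no |
| 3.0 | 7.20 | 25, 40 or 65 | suspend, hospitalise | no rule | no |
| 4.5 or 8 | 7.20 | 40 | suspend, hospitalise | suspend, arterial gas | yes |
| 4.5 or 8 | 7.20 | 25 or 65 | no rule | no rule | **yes** |
| 4.5 or 8 | 7.32, 7.35 or 7.40 | 25 or 65 | no rule | no rule | no |

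The first row is the conflict. Reduce and suspend apply together only at lactate > 3.5 to 4, pH > 7.35 and sVO2 30 to 50%, a band 4 − 3.5 = 0.5 mmol/l wide. The last two rows are the gap: lactate > 4 with sVO2 < 30% or > 50%, at any pH. The fifth row is the serious part of it. Compared with the third row, pH is the same and lactate is higher, yet the mandatory stop has disappeared.

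**Routes that permit a stop but do not require one**

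- Section 11, items 1a to 1f, come under the permissive opening. They include serious adverse events and venous gas abnormalities that meet MALA criteria.
- Section 5.4 lets the investigator discontinue a subject on medical necessity.
- Section 11.1 names abnormal blood safety tests as grounds for interruption, without a threshold.

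**How often the rules are consulted**

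- Metformin arm: 150 patients at 1:1 gives 75, assuming no dropout.
- Scheduled on-treatment venous gases (Figure 1, Exams C): end of run-in plus M3, M6, M9, M12, M15, M18, M21 and M24, which is 9. Total: 9 × 75 = 675.
- Exposure: 25 months × 28 days = 700 days; 75 × 700 / 365.25 = 143.7 person-years.
- Expected MALA cases at the section 2.2.2 rates of 1 to 47 per 100,000 person-years: 143.7 × 1/100,000 = 0.0014, and 143.7 × 47/100,000 = 0.068.

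The documents give no frequency for raised lactate without MALA, so the number of results landing in the conflict band or the gap cannot be estimated. The 675 counts readings, not affected patients.

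**The case against.** The strongest reply concerns the gap. A result with pH below 7.3 and lactate above 4 is by definition a serious adverse event. It must reach the sponsor within 24 hours (section 10.1.10) and be followed to resolution or stabilisation, and section 11 names serious events and MALA-criteria gases as reasons to stop. That is a real safeguard, and few investigators would leave such a patient on metformin. But reporting an event does not suspend the drug. The milder patient, who must be admitted, is also a serious adverse event through hospitalisation, so reporting does not restore the ordering.

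It can also be argued that the plural in item 8's suspension sentence reaches back to the other adverse-event reasons in the list. The sentence is attached to item 8 and closely matches wording in section 10.6. It is too weak a basis for turning the permissive items into requirements.

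On the conflict, the first step in section 10.6 is only to repeat the gas, which is compatible with suspending the drug, and a site that follows item 8 errs on the cautious side. Both points are fair. The collision comes at the next step, where one section reduces the dose and the other requires the drug to be off.

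The limits on weight also stand. The conflict band is narrow, expected MALA cases are far below one, that rate does not measure how often the rules misfire, and the primary analysis is untouched.

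**Conclusion.** The concern holds on both counts. The conflict is confined to lactate above 3.5 and up to 4 mmol/l with pH above 7.35 and sVO2 30 to 50%. The gap is lactate above 4 with sVO2 below 30% or above 50%; at pH below 7.3 it includes results that satisfy the protocol's lactic acidosis definition.

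This should be fixed because safety rules followed as written can give the wrong action, even though the event is rare and investigators may still stop treatment on judgement. The conclusion rests on the wording alone. The counts (675 gases, 143.7 person-years, 0.0014 to 0.068 cases) assume 75 metformin patients with full exposure and the rates quoted in section 2.2.2.

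**What to change.** Amend section 10.6 and section 11, item 8, together:

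1. Use one lactate and sVO2 suspension threshold in both places. Unless the sponsor's clinicians set another limit, take the stricter item 8 rule: suspend and perform an arterial gas at lactate above 3.5 mmol/l with sVO2 30 to 50%, and exclude those results from the dose-reduction rule. State whether patients in the 3.5 to 4 band are also admitted and how they restart, because the two sections differ on this.
2. Extend the suspend-and-hospitalise branch of section 10.6 to lactate above 4 with pH below 7.35 at any sVO2. This brings every result meeting the section 10.1.3 definition under a mandatory stop.
3. State the action for lactate above 4 at pH 7.35 or higher with sVO2 outside 30 to 50%. In the same edit, assign pH of exactly 7.35 with lactate 2 to 4 to one of the section 10.6 rules, since at present neither covers it.

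The cost is a protocol amendment. No scheduled test is added, because venous gas is already taken at these visits. The downside is an occasional extra suspension, arterial gas or admission for raised lactate; the documents do not allow that number to be estimated.

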11.1 Temporary Treatment Discontinuation

In this trial, it is expected that subjects may have one or more treatment interruptions during the unblind, randomized treatment period.

If a subject's IMP treatment must be interrupted for medical or surgical reasons; blood safety test abnormalities; use of a prohibited concomitant medication; or other reasons (e.g., hospital admission for an invasive procedure, a major medical condition, surgery; dental work, or a temporary situation that prevents subject compliance with the IMP administration schedule), the subject's IMP should be resumed as early as the situation allows.

Any IMP interruption of <10 consecutive days will be recorded as missed doses rather than as a temporary interruption of IMP. The subject should immediately inform the investigator of any missed doses reaching or expected to be 2 days or more so that the investigator can continue to monitor the subject's treatments and prepare for a possible 10-day IMP interruption.

An IMP interruption that lasts >10 consecutive days will be recorded as a "10-day Treatment Interruption" on the eCRF and the subject will visit the clinic to collect vital signs and physical exam. Treatment may still be restarted during or after these assessments are completed. If treatment is restarted, and the subject continues to Month 24, the subject will complete the Month 24 visit and scheduled follow-up assessments.

If treatment does not restart, subjects will complete an EoTx visit then 2 follow-up visits (between +8 and +21) must be collected. Assessment at each follow-up visit will include:

1) Perform physical examination, including post-void body weight and height;

2) Record medical/PKD history;

3) Record concomitant medications and ensure subject's treatment meets current standard of care including lifestyle and dietary recommendations, especially for ingestion of at least
2-3 liters of fluid per day as appropriate, unless otherwise directed by study doctor;

4) Assess AEs, if reported;

5) Assess vital signs (include heart rate and blood pressure);

6) Serum pregnancy test for WOCBP (second visit);

7) Collect urine and blood samples for clinical laboratory analyses, including serum creatinine, liver function tests, glucose metabolism parameter, CBC and venous gas analysis (second visit).

11.2 Permanent Treatment Discontinuation

After randomization, a subject may stop treatment permanently before Month 24 for a variety of reasons. Treatment discontinuations may be initiated by a subject who is not satisfied with treatment or may become medically necessary due to AEs or other issues, as determined by the investigator. However, each investigator must comprehensively review the circumstances and offer the subject options for continued treatment to the degree possible.

A subject who permanently discontinues treatment will be recorded as an **IMP discontinuation** on the eCRF. The subject will then enter the follow-up period as though they had reached the Month 24 visit. During the first week of the follow-up period, no procedures will be done. During the last two weeks of the follow-up period, the subject will have a total of 2 samples collected.

After the follow-up period, the subject will continue with all assessments up to and including their scheduled Month 24 visit, but will not be required to complete follow- up beyond that visit.

11.3 Accountability

The investigator or designee must maintain an inventory record of IMP (including investigational, active control, or placebo) received, dispensed, administered, and returned.

12. STATISTICAL CONSIDERATIONS

12.1 Sample Size Determination and Rationale

In TEMPO 3:4, tolvaptan reduced the decline in eGFR from 3.70 to 2.72 ml/min per 1.73 m² per year (26.5%); P=0.001). A post hoc analysis showed that tolvaptan decreased the rate of eGFR decline by 0.40 ml/min per 1.73 m² per year (95% CI, 20.25 to 1.05; P=0.23) in patients with CKD1, by 1.13 (95% CI, 0.61–1.66; P=0.001) in those with CKD2, and by 1.66 (95% CI, 0.83–2.45; P=0.001) in those with CKD3, with a trend for a positive subgroup–treatment interaction (P=0.07). Results for patients in CKD3 were similar when split into CKD3a and CKD3b. Tolvaptan treatment effects on eGFR slope were confirmed by comparing the eGFR values before treatment at baseline and those after discontinuation of study drug, which favored tolvaptan across CKD1 through CKD3. Consistent with the beneficial effects of tolvaptan on the rates of eGFR decline, patients with CKD2 and CKD3 randomly assigned to placebo were more likely to progress to a higher CKD stage at the last follow-up visit than those treated with tolvaptan.

This study will be based upon recruitment of an opportunistic sample given the rarity of the condition and the lack of available studies in the setting.

We plan to recruit a total of 150 patients which are currently within reach of the network coordinated by the proponent and composed by 11 Nephrology Centres. This network treats a total of 1500 (already genetically studied) patients of which we expect (based on standard response rates recognized in the population) acceptance to participate in the study to a value of approximately 40% of patients. These will be then allocated to the experimental and control intervention.

The selected sample is adequate to evaluate a significant reduction in the slope of eGFR at 2 years by 10%, which is a clinically relevant piece of information at the current state of knowledge, as well as a complete assessment of the benefits-harms trade-off of the two interventions.

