	3) Treatment with acarbose, guar gum, cimetidin,
	phenprocoumon, oral anticoagulants, thrombolytic drugs,
	diuretics, ranolazin, cephalexin.
	4) Evidence of active systemic or localized major infection at the
	time of screening.
	5) Hepatic impairment or liver function abnormalities other than
	that expected for ADPKD with typical cystic liver disease during
	the screening period as defined by:
	o AST O ALT >8x UNL
	$ O \qquad AST O ALT > 5x UNL > 2 WEEKS $
	$\begin{array}{c} 0 \\ AST O ALT > 3x UNL E BT > 2x UNL OR INR > 1,5 \\ AST O ALT > 2x UNL E SIGNS AND SYMPTOMS OF \\ \end{array}$
	• AST O ALT >3x UNL E SIGNS AND SYMPTOMS OF
	LIVER DAMAGE (fatigue, anorexy, nausea, vomiting, right hypocondrium pain, fever, jaundice, skin rash, itching)
	6) Acute or chronic disease causing tissue hypoxia (e.g.:
	myocardial failure, severe arythmias, myocardial infarction,
	respiratory failure, liver failure, alcohol acute intoxication,
	alcoholism, dehydration).
	7) Previously diagnosed diabetes already in treatment with other
	hypoglycemic drugs.
	8) Ongoing breast feeding.
	9) Use of any other investigational drug or treatment up to 4
	weeks before enrollment and during the treatment phase.
	10) Known hypersensitivity to metformin and its derivatives.
	11) Psychiatric disorders and any condition that might prevent full
	comprehension of the purposes and risks of the study.
	12) Malignancies within three years before enrolment in the

	study.
	13) HIV, HBV, HCV infection.
	14) Urinary tract obstruction.
INVESTIGATIONAL	Metformin (Zuglimet®) and Tolvaptan (Jinarc®)
PRODUCT(S)	
STATISTICAL	We plan to recruit a total of 150 patients which are currently
ANALYSIS	within reach of the network coordinated by the proponent and
	composed by 11 Nephrology Centres. This network treats a total
	of 1500 (already genetically studied) patients of which we expect
	(based on standard response rates recognized in the population)
	acceptance to participate in the study to a value of approximately
	40% of patients. These will be then allocated to the experimental
	and control intervention.
	The selected sample is adequate to evaluate a significant
	reduction in the slope of eGFR at 2 years by 10%, which is a
	clinically relevant piece of information at the current state of
	knowledge, as well as a complete assessment of the benefits-
	harms trade-off of the two interventions.
STUDY DURATION	Study Duration:
	The trial has a 36 months overall duration, that include a 9 months

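### The claim that 150 patients are adequate for a 10% reduction in eGFR slope is wrong: on the protocol's own figures power is about 8% and the detectable difference about 55%

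*Combined protocol and SAP*

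**What the plan says.** Section 12.1 opens with results from the earlier tolvaptan trial, among them that "tolvaptan reduced the decline in eGFR from 3.70 to 2.72 ml/min per 1.73 m² per year (26.5%); P=0.001", followed by slope differences by CKD stage: "by 1.13 (95% CI, 0.61–1.66; P=0.001) in those with CKD2" and "by 1.66 (95% CI, 0.83–2.45; P=0.001) in those with CKD3". It then explains where the number of patients comes from: "This study will be based upon recruitment of an opportunistic sample given the rarity of the condition", and "We plan to recruit a total of 150 patients which are currently within reach of the network". The section closes with the adequacy claim: "The selected sample is adequate to evaluate a significant reduction in the slope of eGFR at 2 years by 10" per cent, and calls that difference clinically relevant. The Synopsis makes the same statement ("reduction in the slope of eGFR at 2 years by 10" per cent).

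Neither place gives an SD, a power, a formula or an allowance for loss. Section 12.3 sets P<0.05 without saying whether the test is one- or two-sided, and says missing data will be disregarded. Section 4.8 fixes allocation at 1:1, so 150 patients means 75 per arm.

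**The concern.** The number 150 reflects how many patients the network can reach. The 10% sensitivity was then attached to it without a calculation. The precision figures quoted just above the claim look incompatible with it. The CKD stage 3 interval from the earlier trial has a half-width of 0.81 mL/min/1.73 m² per year, about three times the 0.27 that 10% represents here.

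This bears on how the primary result is interpreted. Section 2.2.2 argues that metformin may work as well as tolvaptan. If the trial is non-significant and the protocol says it was adequate for a 10% difference, readers are invited to conclude that the two drugs do not differ by a clinically relevant amount. Ethics committees also rely on such statements.

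**Working it through.** **There is no calculation in the plan to reproduce**, so the check works backwards to the SD the claim would need, and then forwards from the SD the protocol implies.

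**Inputs**
- 75 per arm (Sections 12.1 and 4.8); alpha 0.05 (Section 12.3), taken as two-sided.
- Target effect: 10% of 2.72 = 0.272 per year, tolvaptan being the comparator. If 10% is taken of 3.70, it is 0.37.
- Slope-difference intervals (Section 12.1): CKD3 0.83 to 2.45; CKD2 0.61 to 1.66; CKD1 printed as 20.25 to 1.05, read as −0.25 to 1.05 because the estimate is 0.40.
- Section 8.1.1: 247 patients, 17% of the earlier trial, had eGFR below 60. Total: 247/0.17 ≈ 1,453.
- Assumptions: those 247 are the CKD3 group, and the earlier trial's allocation was 1:1 or 2:1. The documents do not give the ratio, so both are shown.

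**Step 1: SD needed for the claim to hold.** With k = 1.960 + 0.842 = 2.80 and √(2/75) = 0.1633:

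SD = 0.272 / (2.80 × 0.1633) ≈ 0.59; for 0.37, 0.81. With a one-sided 0.05 test, 0.67 and 0.91.

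**Step 2: SD implied by the protocol.** SE = interval width / 3.92 and SD = SE / √(1/n₁ + 1/n₂).
- CKD3: SE = 1.62/3.92 = 0.413.
- CKD2: SE = 1.05/3.92 = 0.268.
- CKD1: SE = 1.30/3.92 = 0.332.
- Three stages pooled by inverse variance: SE = 0.186.
- Overall difference 0.98 with P=0.001: SE = 0.98/3.29 = 0.298.

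**Step 3: what 75 per arm delivers.** Power is two-sided, counting both tails. Detectable difference = 2.80 × SD × 0.1633.

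| SD source | SD | Power, 0.272 | Power, 0.37 | Detectable at 80% | % of 2.72 | Total N for 0.272 |
|---|---|---|---|---|---|---|
| CKD3, 1:1 | 3.25 | 8.1% | 10.7% | 1.49 | 54.6 | 4,476 |
| CKD3, 2:1 | 3.06 | 8.5% | 11.5% | 1.40 | 51.5 | 3,980 |
| Pooled stages, 1:1 | 3.55 | 7.6% | 9.8% | 1.62 | 59.6 | 5,338 |
| Pooled stages, 2:1 | 3.34 | 7.9% | 10.4% | 1.53 | 56.2 | 4,744 |
| Overall P, 1:1 | 5.68 | 6.0% | 6.8% | 2.60 | 95.5 | 13,674 |
| Overall P, 2:1 | 5.35 | 6.1% | 7.1% | 2.45 | 90.0 | 12,154 |

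At a round SD of 3.3:
- SE = 3.3 × 0.1633 = 0.54.
- Power is 8% for 0.272 and 11% for 0.37.
- Detectable difference is 1.51 (56% of 2.72).
- 95% CI half-width is 1.96 × 0.54 = 1.06.
- Patients per arm for 0.272: 2 × (2.80 × 3.3/0.272)² ≈ 2,311.
- Power for tolvaptan's whole quoted effect, 3.70 − 2.72 = 0.98, is 44%.

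**Step 4: how far the assumptions can be pushed.**
- Assumed SD 2.0: power 13%, detectable 0.91 (34%).
- Assumed SD 1.5: power 20%, or 33% for 0.37.
- Assumed SD 1.0: power 38%.
- One-sided 0.05 test: at most 18% over the tabulated SDs and both effect sizes.
- A non-inferiority margin of 0.272 at SD 3.25: 4,476 patients in total.
- An assumed loss of about 15% (64 per arm) at SD 3.25: power 7.6%, detectable 59%.

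**Step 5: a check that uses neither an SD nor an allocation ratio.** The pooled SE of 0.186 is the precision of the earlier trial of about 1,453 patients. Since 0.272/0.186 = 1.46, even that trial would have had about 31% power for a 10% difference.

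**The case against.** The protocol openly calls the sample opportunistic and shows no calculation, so one can argue that the claim is unsupported rather than miscalculated. The SD is derived, not stated. It equates the 247 patients with eGFR below 60 with the CKD3 group, and the pooled value depends on repairing a lost minus sign. The back-calculated figure also absorbs measurement error and incomplete follow-up, so it is an effective SD rather than a pure between-patient one. The overall P=0.001 gives a different SD, perhaps because a less-than sign was lost. A purely truncating type I population could vary less. On loss, recruitment continues until the target is reached, 40% of 1,500 is 600 expected acceptors, and patients who stop treatment are meant to be assessed to Month 24 (Sections 4.5 and 11.2).

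These caveats are fair, and they are reasons to quote a range. They do not rescue the claim. The CKD3 result does not depend on the sign repair. The overall P value only enlarges the SD, or bounds it from above if a sign was lost. Against any gain from a narrower population, slopes over 24 months of 28 days (672 days) would tend to be noisier than those from a 3-year trial. A fall in SD to between 0.6 and 0.9 is not plausible. On loss, a narrower point stands: titration and run-in failures occur after randomisation and get an end-of-treatment visit and a 7-day call (Section 4). They count as randomised but contribute little or no slope, and no number is allowed for them.

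**Conclusion.** The concern holds. The adequacy statement attributes to the design a property it does not have, and figures in the same section contradict it. Power for a 10% difference is about 8% on the stage-specific intervals, and 6% to 12% over all the derived SDs and both readings of 10%. The detectable difference is about 1.4 to 1.6 mL/min/1.73 m² per year on the stage-specific intervals, or 52% to 60% of the tolvaptan slope. This rests on 10% being a relative reduction in slope, a two-sided 0.05 test, 75 evaluable patients per arm (a best case), and SDs back-calculated from the quoted intervals. Because the 10% claim concerns the primary endpoint, it must be corrected.

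**What to change.** Delete the 10% claim from Section 12.1 and from the Synopsis. Keep the account of the sample as one set by availability, and state what it delivers, for example:

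*With 75 patients per arm, a two-sided 5% test and a slope SD of 3.0 to 3.6, the trial has 80% power for a difference of 1.37 to 1.65 mL/min/1.73 m² per year (about 50% to 61% of 2.72), with an expected 95% CI half-width of 0.96 to 1.15.*

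Name the source of the SD, and give the number expected to contribute a slope after titration and run-in loss, with the figures recomputed at that number.

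The cost is wording in two places; no extra patients or procedures are needed. The stated sensitivity becomes less favourable, and the rewording does not cure the limitation. At SD 3.3 the half-width of 1.06 exceeds tolvaptan's entire quoted benefit of 0.98, and readers of a null result should be able to see that in the protocol.
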